GI Index Interpretation,

0.1–1.0: Mild gingivitis

1.1–2.0: Moderate gingivitis

2.1–3.0: Severe gingivitis

For measuring plaque accumulation, the Turesky Modified version contains a basis from 0-5, while also distinguishing severity and location. The same six teeth will be used.

The PI scores will indicate as follows,

0: No plaque.

[figure not shown]
1: Separate flecks of plaque at the cervical margin of the tooth.

2: A thin continuous band of plaque at the cervical margin of the tooth.

3: A band of plaque wider than 1 mm covering less than 1/3rd of the crown of the tooth.

4: Plaque covering at least $1/3^{rd}$ but less than $2/3^{rd}$ of the crown of the tooth.

5: Plaque covering $2/3^{rd}$ or more of the crown of the tooth.

Given the environmental advantages of toothpaste tabs, it is worth exploring the effectiveness of tabs following the action of daily brushing within a 2-week trial period.

After measurements are recorded, comparison of the GI & PI results between tabs and conventional toothpaste will be assessed.

a. Endpoints

Primary endpoints

GI and PI scores between the use of dental tablets and conventional toothpaste.

Secondary endpoints

Satisfaction on user-friendliness of both types of toothpastes.

b. Overall study design

A convenience sample of 40 participants will be randomized into two groups containing 20 individuals each. Randomization will be performed by using a randomization table that is generated by the statistician. Selection of participants will concur to a written consent primarily based on voluntary agreement restricted only to a student consensus.

Group A. Colgate Cavity Protection will be selected as the conventional toothpaste for the control group due to its low abrasivity⁸.

Group B. Colgate Anywhere Toothpaste Tablets will be used as the prime cleansing agent for the experimental group.

Subjects will be instructed to use their normal oral hygiene routine throughout a 2-week timeline. New toothbrushes will be used for both groups—Colgate Slim Soft Gliding Tips Toothbrush, Extra Soft, Compact Head.

Group B will be instructed to use Colgate Anywhere toothpaste tablets where one tablet will be used for brushing. Subjects will gently chew on the tablet to dissolve it and will brush for two minutes at least twice a day. Any residual excess from the tablets are to be spit out. Group A will use Colgate Cavity Protection toothpaste and brush at least twice a day for two minutes.

c. Study Procedures and Schedule

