
Subjects will consent to participate. The examiner will then perform an oral examination to provide an evaluation of plaque and gingival **indexes**. Post 2 weeks, a final assessment will be given by the same examiner done in the exact order and technique as the baseline test. The teeth will be reevaluated with new numeric data, where the scores will be added then divided by the total site surfaces. At the end participants will receive a 10-item satisfaction survey.

- d. Alternative procedures \rightarrow N/A
- e. Deception \rightarrow N/A
- f. Investigational New Drug (IND) \rightarrow N/A

7. INCLUSION / EXCLUSION CRITERIA

Inclusion criteria:

- 1. Subjects are 18 years or older;
- 2. Subjects who will comply with study protocol;
- 3. Subjects who can read and understand the consent form;
- 4. Subjects available during the study period;
- 5. Subjects have more than 20 teeth.

Exclusion criteria:

- 1. Subjects who are pregnant and/or nursing;
- 2. Subjects under the age of 18.

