17. STATISTICAL ANALYSIS

We hypothesize that there will be no statistically significant difference in GI and PI scores between the two groups. To test this hypothesis, we will use an independent sample t-test to compare the difference in GI and PI scores between the two groups. If it is determined that GI and/or PI are not normally distributed, we will proceed with testing our hypothesis with the Mann-Whitney U-test. This hypothesis will be tested at an alpha level of 0.05 and will be two-sided. A sample size analysis was conducted and demonstrated that 20 samples per group were necessary to achieve 80% power to test this hypothesis at an alpha level of 0.05.

18. DATA AND SAFETY MONITORING PLAN (DSMP)

N/A

19. LITERATURE REFERENCES

- 1. Gängler, Peter et al. "In vitro effect of fluoride oral hygiene tablets on artificial caries lesion formation and remineralization in human enamel." *BMC oral health* vol. 9 25. 2 Oct. 2009, doi:10.1186/1472-6831-9-25
- 2. Shaikh, Mohammed et al. "Micro computed tomography analysis of abrasivity of toothpaste tablets compared to conventional toothpaste." *American journal of dentistry* vol. 34,5 (2021): 235-239.
- 4. Chasma, Farida, and Gary Cousin. "Keeping Teeth Clean but Not at the Environment's Expense." *Faculty Dental Journal*, vol. 12, no. 1, 2021, pp. 20–22., https://doi.org/10.1308/rcsfdj.2021.5. https://www.researchgate.net/publication/348155830 Keeping teeth clean but not at the environment's expense
- 5. Moslehzadeh, Kaban. "Quigely Hein Index (modified). *Malmo University*. 27 Apr. 2016, https://www.mah.se/CAPP/Methods-and-Indices/Oral-Hygiene-Indices/Quigely-Hein-Index-modified/
- 6. Lippert F. An introduction to toothpaste its purpose, history and ingredients. *Monogr Oral Sci* 2013; 23:1-14.
- 7. 300 million toothpaste tubes go to landfill. *Br Dent J* 2021; 230-390.

- 8. Löe H. The Gingival Index, the Plaque Index and the Retention Index Systems. J Periodontol. 1967 Nov-Dec;38(6):Suppl:610-6. doi: 10.1902/jop.1967.38.6.610. PMID: 5237684.
- https://aap.onlinelibrary.wiley.com/doi/abs/10.1902/jop.1967.38.6.610?sid=nlm%3Apubmed

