- 9. "Amazon.com: Colgate Anywhere Travel Toothpaste Tablets with Fluoride ..." *Amazon*, https://www.amazon.com/Colgate-Anywhere-Toothpaste-Anti-Cavity-Refillable/dp/B08KQMC5MJ.
- 10. "Cavity Protection Toothpaste: Colgate®." *Cavity Protection Toothpaste* | *Colgate*®, https://www.colgate.com/en-us/products/toothpaste/cc-cavity-protection.
- 11. Moslehzadeh, Kaban. "Quigely Hein Index (modified). *Malmo University*. 27 Apr. 2016, https://www.mah.se/CAPP/Methods-and-Indices/Oral-Hygiene-Indices/Quigely-Hein-Index-modified/
- 12. Wilkins, Esther M., et al. *Clinical Practice of the Dental Hygienist*. 12th ed., Wolters Kluwer, 2017, pp. 372, 400.
- 13. *Amazon.com : Colgate Slim Soft Gliding Tips Toothbrush, extra soft ...* (n.d.). Retrieved August 30, 2022, from https://www.amazon.com/Colgate-Gliding-Toothbrush-Extra-Compact/dp/B07NXDWX78

Schedule of Events

	VISIT 1 (Day/Week/Month)	VISIT 2 (Day/Week/Month)
Informed Consent	X	
Baseline Oral Examination (GI & PI)	X	
Distribution of Product	X	
Post 2-Week Oral Examination (GI & PI)		X
Survey Distribution		X
Weight		
Vital Signs		
Oximetry		
Spirometry		

RESULTS

Table 1. Summary of Gender and Age for Subjects Who Completed the Two-Week Clinical Study

	Nun	Age			
Dentifrice	Male	Female	Total	Mean	Range
Sodium Fluoride Toothpaste1	8	12	20	25	18-36
Sodium Fluoride Toothpaste Tablet2	6	14	20	25	19-30

Table 2. Summary of the Baseline Loe-Silness Gingival Index Scores and Quigley-Hein Plaque Index Scores

	Dentifrice	N	Baseline (Mean±SD)		p-value	95% Confidence Interval	
Parameter				Mean Difference		Lower	Upper
Gingivitis	Toothpaste Tablet	20	1.35±0.26	-0.08	0.47	-0.19	0.13
	Conventional Dentifrice	20	1.37±0.24				
Plaque	Toothpaste Tablet	20	2.80±0.58	0.06	0.665	-0.36	0.38
	Conventional Dentifrice	20	2.78±0.46				

Table 3. Summary of the two-week Loe-Silness Gingival Index Scores and Quigley-Hein Plaque Index Scores

Parameter	Dentifrice	N	Two-Week (Mean±SD)		p-value	95% Confidence Interval	
				Mean Difference		Lower	Upper
Gingivitis	Toothpaste Tablet	20	1.33±0.26	-0.06	0.37	-0.167	0.083
	Conventional Dentifrice	20	1.34±0.18				
Plaque	Toothpaste Tablet	20	2.59±0.49	0.08	0.579	-0.25	0.417
	Conventional Dentifrice	20	2.56±0.48				

Table 4. Summary of Within Group Analysis of Loe-Silness Gingival Index and Quigley-Hein Plaque Index Scores

						95% Confidence Interval	
Parameter	Dentifrice	N	Mean Difference	Percent Reduction	p-value	Lower	Upper

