Gingivitis	Toothpaste Tablet	20	-0.026	1.9	0.765	-0.117	0.064
	Conventional Dentifrice	20	-0.011	0.8	0.936	-0.070	0.048
Plaque	Toothpaste Tablet	20	-0.224	8.0	0.017	-0.453	0.005
	Conventional Dentifrice	20	-0.218	7.8	0.035	-0.391	-0.045

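### Section 17 plans an unadjusted test without saying whether two-week score or change is compared; adjusting for the baseline already collected would cut the standard error by roughly 20–35% against the two-week score, and by less, perhaps nothing, against change

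*Combined protocol and SAP*

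**What the plan says.** Section 17 gives the whole primary analysis in a few lines: "we will use an independent sample t-test to compare the difference in GI and PI scores between the two groups". If normality fails, "we will proceed with testing our hypothesis with the Mann-Whitney U-test". Testing is two-sided at 0.05, and no covariate is named for either test. The primary endpoint in Section 6a reads "GI and PI scores between the use of dental tablets and conventional toothpaste", with no time point and no mention of change.

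The baseline is available. The Schedule of Events lists a GI and PI examination at visit 1 and another at two weeks, and Section 6c says "a final assessment will be given by the same examiner done in the exact order and technique as the baseline test". In the appended results, the arms are compared at baseline (Table 2) and at two weeks (Table 3). Change appears only within each arm (Table 4). No between-arm comparison of change and no baseline-adjusted comparison is shown.

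**The concern.** There are two linked problems. First, the word difference in Section 17 can mean the gap between arms at two weeks or the gap between arms in change. These are different analyses with different standard errors, and the plan leaves the choice open.

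Second, either reading uses the baseline poorly. A test on the two-week score ignores it. A test on change subtracts it with a fixed slope of one, which is too much when the correlation between visits is moderate. A linear model estimates the slope from the data and, apart from a small cost for doing so, is at least as precise as either.

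Neither reading is biased, since allocation is randomized. What is at stake is the width of the between-arm interval with 20 subjects per arm, in a study that hopes to show the products perform alike. A narrower interval would still not establish that, because Section 17 gives no equivalence margin.

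**Working it through.** **The plan's own figure.** Section 17 states 20 per group for 80% power at 0.05 but gives no effect size or SD, so the figure cannot be reproduced. Solving backwards, it corresponds to a standardized difference of 0.886 (normal approximation) or 0.909 (t).

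**Inputs.** SDs, tablet then conventional:
- Baseline (Table 2): GI 0.26, 0.24; PI 0.58, 0.46.
- Two weeks (Table 3): GI 0.26, 0.18; PI 0.49, 0.48.
- Within-arm 95% CIs for change (Table 4): GI −0.117 to 0.064, −0.070 to 0.048; PI −0.453 to 0.005, −0.391 to −0.045.

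**Step 1: SD of change.** The Table 4 intervals are assumed to be paired-t intervals with n = 20, so SD = (half-width / 2.093) × √20. For GI tablet this is (0.0905 / 2.093) × 4.472 = 0.193. The others are 0.126 (GI conventional), 0.489 and 0.370 (PI).

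**Step 2: variances averaged over arms.**
- GI: V0 = (0.26² + 0.24²)/2 = 0.0626; V1 = (0.26² + 0.18²)/2 = 0.0500; Vchange = 0.0266.
- PI: V0 = 0.2740; V1 = 0.2353; Vchange = 0.1880.

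**Step 3: correlation between visits.** r = (V0 + V1 − Vchange) / (2√(V0·V1)).
- GI: 0.0860 / 0.1119 = 0.77.
- PI: 0.3212 / 0.5078 = 0.63.

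**Step 4: standard errors.** Adjusted residual variance = V1 × (1 − r²) × 38/37, which is 0.0210 for GI and 0.1449 for PI. SE = √(2 × variance / 20). Half-widths use t on 38 df (37 when adjusted).

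| | Two-week score | Change | Adjusted |
|---|---|---|---|
| GI: SE | 0.071 | 0.052 | 0.046 |
| GI: 95% CI half-width | 0.143 | 0.104 | 0.093 |
| PI: SE | 0.153 | 0.137 | 0.120 |
| PI: 95% CI half-width | 0.310 | 0.278 | 0.244 |

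Cut against the two-week score: 35% (GI), 21–22% (PI). Cut against change: 11% and 12%. Since 20 × (SE ratio)² gives the equivalent size, the adjusted analysis is worth about 47 (GI) and 32 (PI) per arm on the two-week-score test, or 25 and 26 per arm on the change test.

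**Step 5: sensitivity to the variance source.** V0 and V1 can instead be taken from the printed between-arm CIs in Tables 2 and 3, as (half-width / 2.024)² × 10. Baseline SD stays at 0.250 for GI and becomes 0.578 rather than 0.523 for PI. Two-week SD becomes 0.195 rather than 0.224 for GI, and 0.521 rather than 0.485 for PI. The table covers the four combinations of source. Sampling ranges come from a parametric bootstrap (Wishart, 38 df).

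| | Point estimates, four bases | 95% sampling range, SD basis | 95% sampling range, all bases |
|---|---|---|---|
| GI against two-week score | 34–35% | 19–51% | 18–51% |
| PI against two-week score | 21–27% | 7–38% | 7–44% |
| GI against change | 11–21% | 1–27% | 1–38% |
| PI against change | 8–17% | 1–28% | about 0–34% |

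**Step 6: stress test of Table 4 (SD basis).** If the SD of change is 20% larger than its CIs imply, the cut against the two-week score falls to 24% (GI) and 10–11% (PI), and against change it is 13% and 17%. If 20% smaller, the cuts are 47% and 35%, and 10% and 9%.

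**Conflicts in the source tables.**
- Table 3, GI: the arm means 1.33 and 1.34 differ by −0.01, but the tablet row prints "1.33±0.26 -0.06 0.37 -0.167 0.083", a difference of −0.06 with a CI midpoint of −0.042.
- Table 4, GI conventional: "Conventional Dentifrice 20 -0.011 0.8 0.936 -0.070 0.048", whereas the arm means go from 1.37 to 1.34, a change of −0.03.
- Table 4, PI tablet: "Toothpaste Tablet 20 -0.224 8.0 0.017 -0.453 0.005", whereas the arm means go from 2.80 to 2.59, a change of −0.21. The printed p is also below 0.05 with a CI that includes zero.
- The Table 4 CIs imply paired-t p-values of 0.55, 0.70, 0.055 and 0.016; those printed are 0.765, 0.936, 0.017 and 0.035. The printed p-values are therefore not used.

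**The case against.** The strongest reply is that this is a question of efficiency. The planned test is valid, no type I error problem is shown, and without a margin a tighter interval does not prove similarity. That stands, and it limits the point to precision and clarity.

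It can also be said that the documents lean towards the two-week score: they speak of scores, and Table 3 compares the arms at two weeks. That makes the larger gain the more relevant one. But Table 3 is a result, and the plan itself still leaves the quantity open.

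The between-arm p-values in Tables 2 and 3 do not match their CIs either. The CIs imply about 0.71, 0.96, 0.50 and 0.62; those printed are 0.47, 0.665, 0.37 and 0.579. The printed values may come from the Mann-Whitney fallback, though the documents do not say so. If they do, the cuts above, which are relative to a t-test, do not measure the gain over the test actually run. That limitation stands. It does not alter the SD- and CI-based estimates.

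Finally, the adjusted SE charges one degree of freedom but not the expected cost of chance baseline imbalance, a variance factor of about 1 + 1/36. Including it on the SD basis gives 34% and 20% against the two-week score and 10% and 11% against change. The lower sampling limits against change then reach zero or just below.

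**Conclusion.** The point holds, as a change that should be made, with medium confidence. Section 17 leaves the compared quantity undefined and ignores a baseline measured on every subject. Adjustment would cut the standard error by roughly 20–35% against the two-week score, and that gain stays positive over the sampling range and, taken separately, in the stress test. Against change, the gain is around 10% and could be negligible.

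The sizes rest on the Table 4 intervals being paired-t intervals and on tables that disagree with one another. The GI estimate depends wholly on those intervals. The correlations come from the results and were not known when the plan was written. The case for adjustment did not depend on knowing them, only on the baseline being collected.

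**What to change.** In Section 17, state whether the t-test compares the two-week score or the change. For each index, specify a linear model of the two-week score on treatment group and that index's baseline score, and report the adjusted difference with its 95% CI. Use a robust standard error or a permutation p-value as the sensitivity analysis for non-normality.

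In a plan written before the data, this model would be the primary analysis. Here results are already printed, so the unadjusted test (t-test, or the Mann-Whitney fallback) should remain the planned analysis, with the adjusted model reported beside it and clearly labelled post hoc. The conflicts among Tables 2–4 should be resolved from the subject-level data at the same time.

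The model itself costs one or two sentences, a few lines of code and one degree of freedom. No new data are needed.

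### Section 17 lets the data choose between a t-test and Mann-Whitney by an unstated normality rule, so the quantity tested is not fixed; one baseline-adjusted analysis should replace it

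*Combined protocol and SAP*

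**What the plan says.** Section 17 (Statistical Analysis) states the main test: "we will use an independent sample t-test to compare the difference in GI and PI scores between the two groups". It does not say whether that difference is in the week-2 score or in the change from baseline. It then adds: "If it is determined that GI and/or PI are not normally distributed", "we will proceed with testing our hypothesis with the Mann-Whitney U-test". On the level it says: "This hypothesis will be tested at an alpha level of 0.05 and will be two-sided". Section 6 makes GI and PI the primary endpoints and sets the allocation: "A convenience sample of 40 participants will be randomized into two groups containing 20 individuals each".

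The following are not stated in Section 17 or elsewhere:
- the normality test and its cut-off;
- what is checked (week-2 score or change; each arm, both arms pooled, or residuals);
- whether both endpoints switch when only one fails;
- the estimate and interval to report with Mann-Whitney;
- any adjustment for baseline, although the Schedule of Events has GI and PI examined at both visits.

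**The concern.** The t-test concerns a difference in mean scores. Mann-Whitney concerns the probability that a score in one arm exceeds a score in the other. It becomes a test of a shift in location only if the two arms have the same shape. A plan that moves from one to the other on an unstated reading of the outcome data has not fixed its primary quantity. Two analysts who both follow Section 17 could report different tests on the same data, and GI and PI could end up on different footings. A reader who is given a Mann-Whitney p-value also has no planned effect estimate or interval to set beside it. This matters because Section 5 intends the study to support a recommendation for or against the tablets, which calls for an estimated difference as well as a p-value.

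**Working it through.** **1. The plan's own figure.** Section 17 says a sample size analysis "demonstrated that 20 samples per group were necessary to achieve 80% power to test this hypothesis at an alpha level of 0.05". It gives no effect size or SD, so 20 per group can only be solved backwards: d = (1.960 + 0.842) × √(2/20) = 0.886 SD, or 0.909 SD with the exact t distribution. The figure is neither confirmed nor refuted. The value 0.91 SD serves below as the true shift in the power comparison.

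**2. The switch under the null.** Assumptions: 20 per arm, 10,000 trials per shape, both arms with the same shape and no true difference, and a trigger of Shapiro-Wilk p<0.05 in either arm. The trigger and the shapes are assumptions, because the plan gives none.

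| Shape | Switch fires | t-test error | Mann-Whitney error | Two-stage error | Two tests disagree |
|---|---|---|---|---|---|
| Normal | 9.9% | 5.1% | 5.0% | 5.3% | 2.0% |
| Gamma, shape 4 | 50.4% | 4.9% | 4.9% | 5.5% | 2.4% |
| Lognormal, sigma 0.5 | 77.4% | 4.7% | 5.0% | 5.4% | 3.1% |
| Exponential | 97.3% | 4.6% | 4.7% | 4.9% | 3.5% |

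With the trigger applied to pooled data, two-stage error is 4.7-5.1%. Further runs with equal shapes gave 4.7-5.7%. If the undefined rule let the more favourable test be reported, error would be 6.1-6.4% per endpoint. When the arms also differ in spread and skew, the two tests disagree in up to about 5.5% of null trials. With a true shift of 0.91 SD and equal shapes, they disagree in 5.4% (normal) to 13.3% (exponential) of trials.

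**3. Cost of fixing on means.** At a shift of 0.91 SD, the t-test has about 80% power in all four shapes. Mann-Whitney has 77.4% (normal), 83.4% (gamma), 89.8% (lognormal) and about 93% (exponential). The loss is about 3.5 points under moderate skew and 10 to 13 points under strong skew. Strong skew is less likely here, because GI is an average over 18 surfaces (Section 6) and PI is also averaged over surfaces.

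**4. Gain from baseline.** The detectable difference at 80% power becomes 0.886 × √(1 − r²) SD, where r is the correlation between baseline and week 2. A rough r comes from Tables 2-4: SD of change = SE × √20, and r = (s₀² + s₁² − s_change²)/(2 s₀ s₁).
- Tablet plaque: SE = 0.229/2.093 = 0.109 and SD of change = 0.489. So r = (0.58² + 0.49² − 0.489²)/(2 × 0.58 × 0.49) = 0.59.
- The four rows span about 0.59 to 0.86, the highest being conventional GI.
- Detectable difference: 0.886 × √(1 − 0.59²) = 0.72 SD, falling to 0.45 SD at r = 0.86.

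**5. Tables, checked separately.** The Table 4 intervals were tested as paired t with 19 df. For tablet plaque, t = −0.224/0.109 = −2.05 and p = 0.055, against 0.017 printed. The other three rows also differ (from the CI against printed): tablet GI 0.55 against 0.765, conventional GI 0.70 against 0.936, conventional plaque 0.016 against 0.035.

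Table 3, between arms:
- GI: the means differ by 1.33 − 1.34 = −0.01, the printed difference is −0.06, and the CI midpoint is (−0.167 + 0.083)/2 = −0.042.
- PI: 2.59 − 2.56 = 0.03, against 0.08 printed.
- A t-test from the printed means and SDs gives p = 0.89 (GI) and 0.85 (PI). The CI midpoints give 0.50 and 0.62. The printed values are 0.37 and 0.579. All are non-significant.

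**The case against.** The conditional rule was written in advance, and once its criterion is named each dataset gives one result. Mann-Whitney can be paired with a Hodges-Lehmann shift and interval, so reporting could be made coherent without dropping it. If the products act identically, randomised arms share one distribution and Mann-Whitney holds its level. Under skew the rank test is the more powerful. All of this is correct, and it keeps the point modest. It does not rescue the text as it stands, which names neither the criterion nor the accompanying estimate.

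A reader might infer two stronger things.
- **That switching seriously inflates type I error.** Simulation with equal means, SDs of 0.18 and 0.26 (the Table 3 GI values) and skew only in the arm with the larger SD does give about 9%. But Mann-Whitney used alone, with no switch, also gives 9.0% there. The excess comes from judging a rank test against a null about means only. With normal arms and the same unequal SDs, the two-stage error is 5.4-5.6%.
- **That Table 4 shows the switch at work.** Table 4 is a within-group analysis, and the planned switch concerns independent groups. The tables name no test. The mean differences in Tables 2 and 3 also fail simple subtraction, which no choice of test explains. Reporting error is at least as plausible a cause.

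**Conclusion.** The concern holds as a defect of specification. Section 17 leaves the primary quantity to be chosen after the data are seen, by an unstated rule, with no estimate tied to one of the two tests and no stated use of the baseline scores. Its size is modest: error of about 4.7-5.7% when the arms share a shape, and disagreement between the tests in about 2-6% of null trials. These figures rest on the assumed Shapiro-Wilk trigger, the assumed shapes and 20 per arm. The documents do not support a claim of serious alpha inflation, nor a claim that the switch altered the trial's result: the between-arm comparisons are non-significant on every calculation above. The mismatch between p-values and intervals in Table 4 is real, but it is a separate within-group reporting fault of unknown cause. Deleting the switch would not by itself repair it.

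**What to change.** In Section 17, delete the normality-triggered switch. Name one primary analysis for each endpoint: a linear model of the week-2 score on arm and baseline score, whatever the distribution looks like, with the adjusted mean difference, its 95% CI and its p-value all taken from that model. Keep Mann-Whitney as a labelled sensitivity analysis. Because results are already printed, label any re-run on these data as post hoc.

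Separately, correct Tables 2 to 4 so that each row's estimate, interval and p-value come from one named method and the mean differences agree with the printed means.

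The cost is two sentences, a re-run and a table check. The sample size need not change. The drawback is lower power than a rank test under skew: about 3.5 points in the moderate case simulated and more if skew is strong. Baseline adjustment works in the other direction.

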5. OBJECTIVES AND PURPOSE

Due to its travel-friendly size and eco-friendliness, toothpaste tablets have gained popularity among the green people. Green people are those who aim to achieve sustainability. Despite toothpaste tablets' many merits, there is only scarce information on the efficacy, consumer satisfaction, cost, and benefits. Therefore, the purpose of our study is to evaluate the efficacy of toothpaste tablets when compared to conventional toothpaste in removing plaque. We aim to evaluate this by, measuring gingival index (GI) and the plaque index (PI) on subjects that have been either using the tabs or toothpaste.

We hypothesize that there will be no statistically significant difference in GI and PI scores between the two groups. The results of the study will be highly significant as it will serve as a strong piece of evidence to recommend or not to recommend this newly developed product that has the potential to keep our planet safe from non-degradable plastic.

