12. POTENTIAL BENEFIT(S)

Potential benefits to subjects and society would be to provide that there is not a clinical or statistical difference in the efficacy of dental tablets versus conventional toothpaste. Providing data that presents no difference in using either tablets or toothpaste may incline the public to switch to an eco-friendlier dentifrice, thus reducing waste. Potential benefits outweigh the risks of this study due to the very low risk involved.

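### Do two primary indices, GI and PI, tested under a single alpha of 0.05, need a multiplicity adjustment?

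*Combined protocol and SAP*

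**What the plan says.** Section 6a gives the primary endpoints as "GI and PI scores between the use of dental tablets and conventional toothpaste", with no ranking of the two. Section 5 names the same pair as the measure of efficacy.

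Section 17 states one expectation for both: "We hypothesize that there will be no statistically significant difference in GI and PI scores between the two groups". On the test it says "we will use an independent sample t-test to compare the difference in GI and PI scores between the two groups", with a Mann-Whitney fallback that is triggered if either or both indices are non-normal. On the error rate it says "This hypothesis will be tested at an alpha level of 0.05 and will be two-sided". On size it says that "20 samples per group were necessary to achieve 80% power to test this hypothesis at an alpha level of 0.05", without naming the index, effect or SD behind that figure.

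No section contains an alpha split, a testing order, a composite, or a statement of how the two results combine. The RESULTS section reports the indices separately. The table headed "Table 3. Summary of the two-week Loe-Silness Gingival Index Scores and Quigley-Hein Plaque Index Scores" gives each its own p-value and 95% confidence interval, with no joint verdict. Section 12 states the hope as being to "provide that there is not a clinical or statistical difference in the efficacy of dental tablets versus conventional toothpaste".

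**The concern.** Alpha is attached to the hypothesis, and the hypothesis covers two indices that are tested separately. A statement that the groups do not differ on GI and PI is, read literally, contradicted by a difference on either one. Two unadjusted chances to contradict it at 5% each give a joint error rate above 5%, so the plan would not deliver the rate it states.

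There is also a question of interpretation. If one index were significant and the other not, the plan would not settle whether its hypothesis stands. The 80% power claim has the same looseness, because it does not say on which index, or under which rule, power was calculated. At stake would be a false report that the products differ, or a choice of decision rule made after seeing the data.

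**Working it through.** **Inputs.** Two primary indices (Section 6a); two-sided alpha 0.05, 20 per group and 80% power (Section 17); two-week means and SDs (Table 3); within-group changes and intervals (Table 4). The correlation between the two test statistics is not in the documents, so a range is assumed.

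**The plan's own figure.** The 20 per group cannot be reproduced, because no effect or SD is given. It can only be inverted. By normal approximation the detectable difference is (1.960 + 0.842) × √(2/20) = 0.886 SD; by the exact t-test it is 0.909 SD. The error rates below depend only on alpha and correlation, so this gap does not affect them.

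**Error rate under three decision rules, when neither index truly differs.**

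1. *Either index refutes.* With independent tests the rate is 1 − 0.95² = 0.0975. With correlation ρ it is 1 − P(|Z₁| < 1.96, |Z₂| < 1.96) for a bivariate normal pair.
2. *Both indices must differ.* The rate is 0.05 + 0.05 minus the rate under rule 1.
3. *One conclusion per index.* The rate is 5% for each claim, whatever ρ is.

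| Assumed ρ | Either | Both | Per index |
|---|---|---|---|
| 0 | 9.75% | 0.25% | 5% |
| 0.5 | 9.07% | 0.93% | 5% |
| 0.7 | 8.35% | 1.65% | 5% |
| 0.9 | 7.04% | 2.96% | 5% |
| 0.95 | 6.46% | 3.54% | 5% |
| 0.99 | 5.66% | 4.34% | 5% |

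Simulated t-tests with 20 per group (200,000 runs per correlation) agree for the first rule: 9.8%, 9.1%, 8.4% and 7.0% at ρ = 0, 0.5, 0.7 and 0.9. Only the first rule exceeds the stated 5%.

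**What an adjustment would cost.** Assume each index has 80% power unadjusted, that is, a true difference of 0.909 SD (the plan does not say this). Under Holm the smaller p-value is compared with 0.025 and, if that is met, the larger with 0.05.

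- Only one index differs: power is about 70% (0.705 at alpha 0.025).
- Both differ: power per index is about 75–77%.
- Both differ, at least one significant: this falls from 96–85% to 91–77% as ρ goes from 0 to 0.9.
- Restoring 80% when only one differs takes about 25 per group (0.794 at 24, 0.813 at 25).

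**Effect on the reported results.**

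- Printed p-values: 0.37 (GI) and 0.579 (PI). After Holm, 2 × 0.37 = 0.74 for both.
- Recomputed from the Table 3 means and SDs: for GI, SE = √((0.26² + 0.18²)/20) = 0.0707, t = −0.01/0.0707 = −0.141, p = 0.888. For PI, SE = √((0.49² + 0.48²)/20) = 0.1534, t = 0.03/0.1534 = 0.196, p = 0.846. Rounding of the inputs cannot bring these below 0.774 and 0.794. After Holm both are 1.00.
- If change from baseline is compared instead, with SEs recovered from the Table 4 intervals: for GI, (−0.026 + 0.011)/0.0516 = −0.29, p about 0.77. For PI, (−0.224 + 0.218)/0.137 = −0.04, p about 0.97.

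No between-group comparison is near 0.05 on any of these routes.

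**The case for a change.** The best case for a change is that Section 17 gives its 5% to the hypothesis and not to each test, that the hypothesis is joint, and that a plan should say in advance what refutes it. A few sentences would do it, and a null result does not excuse an unstated rule. All of this is fair as far as it goes. The decision rule is unstated, the power statement names no endpoint, and a plan that said both would be tidier.

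It does not establish an error. The step from the joint wording to a rule under which either index refutes is an inference, and the plan's other features point at least as much to separate conclusions: normality is judged index by index, and Table 3 gives each its own p-value and interval. With only two tests, both fully reported, a reader can see the whole family and apply a joint standard if one is wanted.

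Nor does the proposed remedy clearly improve matters. The team expects and hopes for no difference, so leaving the tests unadjusted is the stricter course for its own claim. Holm would move the plan towards the hoped-for answer. Because results are already in the document, the rule would also be post hoc and could not supply prespecified error control.

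Two neighbouring points should not add weight here. One is that non-significance does not by itself show that the products are alike. The other is that the Table 3 mean differences (−0.06 and 0.08) do not match the differences of the printed means (−0.01 and 0.03). Both are separate from multiplicity.

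**Conclusion.** No change to the plan follows. The text does leave open how GI and PI combine, but analysts fill that gap sensibly by reporting each index as its own comparison at 0.05 with its interval, which is how Table 3 presents them. The inflation to between 9.75% (ρ = 0) and 7.0% (assumed ρ = 0.9; 5.7% at 0.99) arises only under an either-index rule that the plan does not state. Under the other two rules each claim is held at 5% or less.

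Adjustment is a trade-off and not a correction. It guards against a false difference, which is not the error that threatens this trial's intended conclusion. On the assumption of 80% power per index, it costs roughly 3 to 10 percentage points of power for each index that truly differs (80% falling to about 70–77%). No between-group conclusion moves, whether the p-values are taken as printed, recomputed from the means and SDs, or approximated from the changes.
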